8.2.4 Childbearing potential

It must be recorded in the eCRF whether female subjects are of childbearing potential. Pregnancy testing must be performed on female subjects of childbearing potential as described in Section [8.5.2.7](#). Female subjects of childbearing potential, and partners of male subjects of reproductive age, must be instructed to use adequate contraceptive methods throughout the trial and until at least 16 days after last trial drug administration.

Female of non-childbearing potential is defined as:

- Female who has undergone a hysterectomy, bilateral oophorectomy or bilateral tubal ligation
- Postmenopausal defined as no menses for 12 months without an alternative medical cause
- Other medical reasons preventing childbearing potential

8.2.5 Body measurements

8.2.5.1 Height and body weight

The height (in cm, without shoes) and body weight (in kg, without shoes and overcoat) of the subject will be recorded at screening.

Body weight will be measured at regular intervals throughout the trial (see section [2](#)). It is preferable to measure body weight at the same time of day, using the same scale from visit to visit.

8.3 Efficacy assessments

8.3.1 CT scans

Quantitative CT scans will be performed at randomisation (before first trial dose administration) and at week 51+ 4 days to determine cross-sectional TAT, SAT and VAT adipose tissue

compartments. **Note:** This CT scan may be performed at the screening visit instead of at the randomisation visit, if a CT scan is required to confirm eligibility in relation to exclusion criterion # 8.

8.3.2 Patient reported outcomes

Patient reported outcomes (PROs) will be assessed at randomisation and in week 32 and week 51 (see section 2) using the Treatment Satisfaction Questionnaire for Medication - 9 items (TSQM-9)²⁷. At randomisation, subjects will state their satisfaction with their pre-trial GH therapy, as they have not yet received trial medication.

The TSQM-9 is a generic questionnaire that measures a subject's satisfaction with medication. Items are rated on a 5- or 7-point scale according to the subject's experience with the medication and the concepts covered are satisfaction with the effect of the medication, convenience, confidence and global treatment satisfaction.

By using the TSQM-9 it will be possible to assess the subjects' satisfaction with medication.

The PRO questionnaire will be a self-administered questionnaire, to be completed by the subject without assistance of the site personnel. The questionnaire should be completed after all fasting related activities are completed but before any other trial related activity at each applicable visit. Written instructions on how to complete the questionnaire will be provided to the subject. Subjects who cannot complete the questionnaire themselves due to physical limitations may receive assistance with completion of the questionnaire. After completion the PRO must be reviewed by the investigator on the same day for potential AEs, including any overall change in health and concomitant medication. When reviewing the PRO questionnaire for AEs the investigator should not influence nor question the subject on the content of the subject's response to PRO questions. Review of the PRO must be documented either on the front page of the documents and/or in the subject's medical record. If clarification of entries in the PRO questionnaire is needed, the subject should be questioned and a conclusion made in the subject's medical record. Only the subject can make changes in the PRO. Care should be taken not to bias the subject. Filled in questionnaires will be sent for central data entry into the clinical database.

8.4 Safety assessments

8.4.1 Adverse events

Adverse events (AEs) must be reported at each visit in accordance with the procedures outlined in Section 12.

8.4.1.1 Medication error

If a medication error is observed during the trial, the following information is required and a specific event form (medication error form) must be completed in the eCRF in addition to the AE form:

- Trial product(s) involved
- Classification of medication error
- Whether the subject experienced any adverse event(s) as a result of the medication error
- Suspected primary reason for the medication error

For definition of medication errors and reporting timelines, see Section [12.1.4](#).

8.4.1.2 Adverse events requiring additional data collection

For some AEs additional data collection is required and specific event forms must be completed in the eCRF in addition to the AE form.

In case any of these events fulfil the criteria for a SAE, please report accordingly, see Section [12](#).

For the following AEs additional data collection is required:

Injection site reactions:

Injection site reactions will be evaluated during the trial (see section [2](#)). If suspicion of an injection site reaction occurs between site visits the subject should be instructed to call the site as soon as possible for further guidance. An unscheduled visit may take place at the investigators discretion.

At all site visits injection site reactions will be evaluated by the investigator by visual and manual inspection of injection sites; at randomisation, injection site reactions will be evaluated after trial drug administration.

If an injection site reaction fulfils the criteria for an AE, it should be reported on the AE form. Additionally, a specific injection site reaction form must be completed in the eCRF.

In the event of an injection site reaction, additional assessments will be performed until resolution, as judged necessary by the investigator. The following results will be recorded in the eCRF:

- Burning
- Pain
- Numbness
- Itching
- Redness
- Induration
- Dimpling (small cavities)
- Swelling
- Macula
- Haematoma
- Bleeding
- Other symptoms/findings

In addition to reporting the site reaction on the AE form and on the injection site reaction form, digital photos must be taken of the injection site at the time of identification and hereafter as often as judged necessary by the investigator. Should injection of trial product require more than one injection, all injection sites should be evaluated. The photos should include trial ID and subject number, as well as date of photo, actual time of photo (24h format) and a ruler for injection site measurement. Copies of all photos will be evaluated by an external dermatologist and subsequently transferred to Novo Nordisk.

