5.2 Rationale for trial design

The inclusion of the active controlled arm in the open-labelled design is to compare safety including local tolerability (i.e. injection site reactions) of somapacitan to daily Norditropin[®] FlexPro[®] treatment. The open-labelled design is chosen because a blinded design would not be technically feasible due to the difference in injection frequency, and in order to be able to compare the degree of subject satisfaction related to daily vs. weekly injections, which would not be possible if a double-dummy design was applied.

Trial NN8640-4043 showed that at baseline and during the titration period, the number of patients with IGF-I standard deviation score (SDS) below -2 was different in the somapacitan group than in the Norditropin[®] FlexPro[®] group. Based on these data, the following will be implemented:

1. Addition of an inclusion criteria ensuring that only patients with IGF-I levels between -2 SDS and +2 SDS will be included.
2. Addition of one titration visit, allowing up to five opportunities for dose adjustments.

No positive test results for anti-somapacitan antibodies or anti-hGH antibodies were reported in trial NN8640-4043. Therefore, antibody samplings will be performed only at randomisation and at the final follow-up visit.

The somapacitan PK modelling results from trial NN8640-4043 showed steady state from 2 weeks and forward following initial dose as well as following each dose adjustment, allowing a titration schedule in alignment with normal clinical practise and facilitating patient recruitment.

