5.3 Treatment of subjects

Time of injections:

- Somapacitan subjects will inject themselves once a week s.c. in the morning no later than 10 AM to ensure consistency of PK/PD with previous trials. On site visit days this can be extended until 12 PM (noon). Trial drug may not be administered in the morning before relevant visit procedures have been performed (see section 2).
- Norditropin[®] FlexPro[®] subjects will inject themselves daily s.c. in the evening (to reflect standard treatment practice) throughout the trial and only in the morning (no later than 12 PM (noon) and at least 12 hours after injection the evening before) during observed trial drug administration. Injections with Norditropin[®] FlexPro[®] the night before blood sampling for anti-hGH antibodies must occur at least 12 hours prior to sampling.

The first dose will be administered by the subject on Day 0 (at randomisation). The first dose will be fixed, and will be provided by the electronic case report form (eCRF). The last dose will be

administered by the subject at home, for subjects in the somapacitan treatment arm prior to the visit at week 51+4 days and for subjects in the Norditropin[®] FlexPro[®] arm 3 times after that visit (so that Norditropin[®] FlexPro[®] will be administered 7 times in week 51). No trial drug will be administered in Week 52 prior to the follow-up visit. The maximal treatment duration for a single subject is 52 weeks.

Subjects in both arms will be trained in the use of the pen-injector and inject themselves with trial drug under the supervision of the site staff at the visits where administration is observed, and will inject themselves at home.

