5.3.1 Dose titration

During the first 20 weeks the dose will be titrated every fourth week starting from week 4. The last dose adjustment will be done at week 20. This allows five opportunities for dose adjustment (weeks 4, 8, 12, 16 and 20). Dose titration is based on insulin-like growth factor-I standard deviation score (IGF-I SDS) values used for calculation of the next dose. The dose adjustment calculations will provide the new doses for the subjects in the eCRF. IGF-I, insulin-like growth factor binding protein – 3 (IGFBP-3) and IGF-I SDS results will not be made available to the investigator during the trial.

The dose administered to the subject must be entered in the IWRS.

Subjects will come to the clinic 3 weeks and 3 days after the previous dose adjustment visit for an IGF-I, IGFBP-3 and PK blood sample draw. Handling deviations from this schedule is described in section [5.3.5](#). The dose adjustments are performed at weeks 4, 8, 12, 16 and 20, i.e. four days after the IGF-I titration samples have been collected. Dose adjustments will be provided over the phone, except for the last dose adjustment (week 20) which will happen at site. After last dose adjustment visit (week 20), the individual dose level is fixed.

Besides the IGF-I based dose adjustment during the titration period, dose reduction can be considered during the entire trial period (including the titration period) at the investigator's discretion for safety concerns. If adverse events with a probable relationship to the trial drug are persistent but continuation in the trial is acceptable, as judged by the investigator and subject, dose reduction in steps of 25% can be considered. If, after consecutive dose reduction steps, AEs still persist, the subject's treatment may be discontinued or the subject may withdraw as described in section [6.4](#) and [6.5](#).

If a subject reports symptoms of GH related AEs at a dose adjustment visit, the dose titration in the eCRF should be performed prior to potentially reducing the dose by 25% (performing the dose reduction in the eCRF), as the IGF-I based titration might reduce the dose.

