8.6.2 Subject diaries

From randomisation a diary will be handed out to the subjects at relevant visits (see section [2](#), Flow chart). After randomisation, the completed diaries will be collected at regular intervals. The subject should be instructed by the site staff to complete the diary with the following records:

- Drug compliance (from randomisation): The subject will be asked to record date, time and dose of injections and any missed dose
- AEs (incl. injection site reactions)
- Concomitant medication, including changes

Review of diaries must be documented either on the front page of the documents and/or in the subject's medical record. If clarification of entries or discrepancies in the diary is needed, the subject must be questioned and a conclusion made in the subject's medical record. Care must be taken not to bias the subject. Data from the subject diaries will be entered in the eCRF by the site staff.

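### At the nine on-treatment site visits, injection sites are inspected 3 to 7 days after a somapacitan injection but about half a day after a Norditropin one, so inspection-detected reactions are not comparable between arms

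*Combined protocol and SAP*

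**What the plan says.** **Inspection.** Section 8.4.1.2 requires: "At all site visits injection site reactions will be evaluated by the investigator by visual and manual inspection of injection sites". The only link to dosing is for the first visit: "at randomisation, injection site reactions will be evaluated after trial drug administration". Nothing similar is set for later visits.

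**Dosing (section 5.3).** For the weekly arm: "Somapacitan subjects will inject themselves once a week s.c. in the morning no later than 10 AM". On visit days, "Trial drug may not be administered in the morning before relevant visit procedures have been performed". For Norditropin: "subjects will inject themselves daily s.c. in the evening".

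**Visits.** Section 5.3.1 sets the titration samples: "Subjects will come to the clinic 3 weeks and 3 days after the previous dose adjustment visit". The flow chart (section 2) puts the on-treatment site visits after randomisation at 3W+3D, 7W+3D, 11W+3D, 15W+3D, 19W+3D, 20W, 32W+4D, 42W and 51W+4D, with follow-up at 53W.

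**Other routes of detection.** The diary (section 8.6.2) names injection site reactions as an item to record. Section 12.2 requires subjects to be asked about adverse events at every contact. The flow chart marks injection site reactions at the phone visits as well. Section 8.4.1.2 tells subjects to call if they suspect a reaction between visits, and leaves an unscheduled visit to the investigator.

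**Use.** Injection site reactions are part of the primary endpoint (sections 4.2.1 and 17.3). Section 5.2 gives comparison of local tolerability with daily Norditropin as a reason for the control arm. Section 17.3 summarises adverse events descriptively by treatment, system organ class and preferred term, and does not separate them by how they were found.

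**The concern.** Inspection is the only scheduled objective examination of the injection sites, and the visit calendar ties it to the weekly dosing cycle. A somapacitan site has had at least three days to clear before anyone looks, while the newest Norditropin site is less than a day old. The signs most likely to be missed are mild ones that a subject may not notice or report; section 8.4.1.2 lists induration, dimpling and macula among the findings to record.

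If reactions from all routes are pooled by arm, as section 17.3 plans, a lower somapacitan count could reflect tolerability, the timing of inspection, or both. The report would give no means of telling them apart, on a comparison that section 5.2 puts forward as a purpose of the control arm.

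**Working it through.** **1. Check the calendar against the plan.** Take somapacitan on days 0, 7, ..., 357 and Norditropin on days 0 to 363. V15 (51W+4D) is day 361 and V16 (53W) is day 371.
- Week 51 is days 357 to 363, which gives 7 Norditropin doses. Those on the evenings of days 361, 362 and 363 come after V15, which gives 3. Both match section 5.3.
- Dose-free time before V16 is 371 − 357 = 14 days for somapacitan and 371 − 363 = 8 days for Norditropin. These match the minimum gaps that section 8.1 sets for subjects who stop early.

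**2. Time from latest injection to inspection.**

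| Visit | Somapacitan | Norditropin |
|---|---|---|
| V2 | after dosing | after dosing |
| V3, V5, V7, V9, V11 | 3 days (4 with the +1 day window) | about 12 h |
| V12 (20W), V14 (42W) | 7 days | about 12 h |
| V13 (32W+4D), V15 (51W+4D) | 4 days | about 12 h |
| V16 (53W) | 14 days | 8 calendar days |

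The 12 hours is inferred. An evening dose between 19:00 and 23:00 and an inspection between 08:00 and 12:00 give 9 to 17 hours. The 7 days at V12 and V14 assumes that inspection precedes that day's dose.

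**3. Chance that a reaction is still present at inspection.** The documents give no duration, so assume it is exponential with mean m days. A reaction at a site d days old is still present with probability exp(−d/m).
- Somapacitan: average over d = 3, 3, 3, 3, 3, 7, 4, 7, 4.
- Norditropin, latest site: d = 0.5.
- Norditropin, all sites of the past week: average over d = 0.5, 1.5, ..., 6.5.

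Example with m = 2:
- Somapacitan: (5 × 0.223 + 2 × 0.135 + 2 × 0.030)/9 = 0.161.
- Norditropin, latest site: exp(−0.25) = 0.779.
- Norditropin, past week: (0.779 + 0.472 + 0.287 + 0.174 + 0.105 + 0.064 + 0.039)/7 = 0.274.

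| Mean duration | Somapacitan | Norditropin, past-week sites | Norditropin, latest site only |
|---|---|---|---|
| 1 day | 3% | 14% | 61% |
| 2 days | 16% | 27% | 78% |
| 3 days | 28% | 39% (38.5) | 85% |
| 7 days | 57% | 63% | 93% |

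The past-week column is the fairer comparator, because section 8.4.1.2 does not limit inspection to the newest site. The gap is then about 6 to 11 percentage points.

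**4. Fixed durations instead.**
- Any fixed duration above half a day and up to 3 days: 0 of 9 somapacitan inspections would find the reaction, while 1 to 3 of the 7 past-week Norditropin sites would still show it.
- 3.25 days: 5/9 = 56% for somapacitan against 3/7 = 43% for Norditropin. The direction reverses.
- 4.25 days: 7/9 = 78% against 4/7 = 57%. Again reversed.

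**5. Share of all reactions over the trial that inspection would find.** Assume the same reaction chance for each of 52 somapacitan and 364 Norditropin injections, and count each reaction at its next inspection from V3 to V15. For a mean of 1 day this is about 9 × 0.032/52 = 0.6% against 9 × 7 × 0.137/364 = 2.4%. For means of 2, 3 and 7 days it is 2.8% v 4.8%, 5.2% v 7.2% and 14.3% v 16.0%. The gap is about 2 points throughout.

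**The case against.** A reader might infer that the primary endpoint is collected unequally in favour of somapacitan because inspection is the only systematic assessment. The documents do not support that. Questioning at each contact, the named diary item, the phone-visit marks in the flow chart and the instruction to call apply to both arms and can pick up short-lived reactions that the subject notices. Step 5 shows that inspection would find only a small share of short reactions in either arm, so most must come from these other routes.

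Nor is the mismatch universal or its direction settled. V2 is inspected after dosing in both arms, and V16 is about 14 against 8 days. Section 8.6.1 provides for observed injections after training, but the flow-chart rows that would place those visits are not in the text available for this review. At such a visit, inspection could follow the dose. The starkest contrast (3% v 61%) uses only one of seven weekly Norditropin sites, and step 4 shows that the sign can change.

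The primary analysis is also descriptive, with no test or margin, and the sample size has no formal basis. That limits the consequence, but descriptive reporting does not make unequally timed examinations comparable.

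Finally, resting the comparison on subject reports alone would bring in knowledge of treatment, since the trial is open-label. A per-injection prompt would also be asked 364 times in one arm and 52 in the other. Both points stand, and they shape the fix.

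**Conclusion.** At nine of the eleven site visits from V2 to V16, scheduled inspection comes 3 to 7 days after the latest somapacitan injection and roughly half a day after the latest Norditropin injection. Neither section 8.4.1.2 nor section 17.3 deals with this. Inspection-detected reactions are therefore not comparable between arms. Under-counting with somapacitan is plausible if reactions are short-lived: a shortfall of about 6 to 11 points per reaction against past-week Norditropin sites under exponential durations, and about 2 points as a share of all reactions. These sizes rest on assumed durations, nominal visit days, inspection before dosing at 20W and 42W, and an inferred half-day interval for Norditropin.

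It goes too far to conclude that the primary endpoint as a whole is biased, or that any bias must favour somapacitan. The other detection routes run in both arms, and the direction depends on reaction duration and on which sites are examined, neither of which the documents specify. This is a modest weakness in ascertainment and reporting.

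**What to change.** **Form.** On the existing injection site reaction form, record how the reaction was first detected (subject report by diary, call or questioning, or investigator inspection) and the time since the injection at that site.

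**Analysis.** In section 17.3, or in the SAP if one is written, add a table of injection site reactions by treatment and detection source. Show both sources side by side. State that a between-arm difference in inspection-detected reactions will not on its own be read as a difference in tolerability. Because the trial is open-label, the subject-reported set should accompany the inspected set and not replace it.

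**Optional.** Add a yes/no reaction tick to the diary line for each injection, where already "The subject will be asked to record date, time and dose of injections and any missed dose". It adds some diary burden and prompts the daily arm seven times as often (364/52 = 7), so it should be read with that in mind.

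**Cost.** A small addition to an existing form (source and timing) and one extra table. Dosing and visits are unchanged.

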8.4.2 ECG

A standard 12-lead ECG will be performed while the subjects are in supine position according to the flow chart (see section [2](#)). The investigator will evaluate the ECG recordings and classify them according to the following categories:

- Normal
- Abnormal
 - Was the result clinically significant? (Yes/No)

At the screening visit, ECGs classified as abnormal and clinically significant will be recorded as concomitant illnesses. Worsening of ECGs will be recorded as AEs if they are evaluated as abnormal and clinically significant at a time point after the screening procedure. If a 12-lead ECG has already been performed and is available ≤ 90 days before randomisation, the procedure need not be repeated. It must be documented in the subject notes that the reason for performing the ECG was not related to the present trial. ECG recordings must be dated and signed by the investigator to document data review.

8.4.3 Physical examination

A physical examination of the following body systems will be performed at screening, randomisation and throughout the trial (see section [2](#)):

- Head, ears, eyes, nose, throat, neck
- Respiratory system
- Cardiovascular system
- Gastrointestinal system, including mouth
- Musculoskeletal system
- Central and peripheral nervous system
- Skin
- Lymph node palpation

The investigator will evaluate the findings from the physical examination and classify them as follows:

- Normal
- Abnormal
 - Was the result clinically significant? (Yes/No)

At the screening visit, physical examination classified as abnormal and clinically significant will be recorded as concomitant illnesses. Worsening of physical examination findings from the screening visit will be recorded as AEs.

